A total of 24 not well controlled type 2 diabetic subjects with Periodontitis presenting for medical care at LLU Health will be recruited for the study (see power analysis under statistical section). An additional 6 subjects will also be recruited to compensate for subject attrition. Subjects will be divided into two group based on their medical needs: HBO therapy and Non HBO therapy. For all subjects demographic data (age, gender, ethnicity, smoking history, alcohol use history, BMI, current medication list) and oral health habits will be obtained. HBOT subjects will be recruited first and control subjects (non HBO group) will be recruited after to match the HBO subjects on all parameters including HbA1c level to minimize bias.

Inclusion Criteria:

Diabetic patients must meet the following inclusion criteria:

1. An established diagnosis of DM type 2 (HbA1c =>7%).
2. Subjects must have a minimum of 10 permanent teeth.
3. Age range 35 year or older.
4. All subjects must be registered patients at LLU Health.

Exclusion Criteria:

Individuals with the following conditions may NOT participate in the study:

1. Well-controlled type 2 diabetics (HbA1c <7%) and type 1 diabetic patients.
2. Other systemic conditions with known association with periodontitis, e.g. AIDS, Down's syndrome, current smoker, head and neck radiation, Xerostomia, currently under chemotherapy.
3. Intra-oral conditions present which might interfere with accuracy of periodontal probing, e.g. gingival overgrowth, orthodontic wires, excessive calculus.
4. Not a registered patient at LLU Health.
5. Overweight/obese individuals (BMI greater than 45 %)
6. Pregnancy or lactation

[figure not shown]
QUESTIONNAIRE:

Oral Health Interview: subjects will be interviewed regarding personal and professional dental care habits and cigarette smoking habits.

Study Plan:

Group	Not eligible for HBOT N=15	Eligible for HBOT N=15
Medical History Review Medical Assessments	Yes	Yes
Baseline HbA1c	Yes	Yes
Baseline Periodontal Evaluations	Yes	Yes
SRP	Yes	Yes
HBO Therapy	No	Yes (20-40 daily treatments for 8 weeks)
Final Periodontal Evaluation (12 weeks after SRP)	Yes	Yes
Final HbA1c (12 weeks after SRP)	Yes	Yes

Note: subjects in both groups will be receiving any needed medical care

CLINICAL EVALUATIONS

Medical Assessments:

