For bacterial DNA extraction, 44 mL of each sample will be taken, and 0.5% polysorbate 20 and 1 mL of protease K (10 mg/mL) will be added. The samples will be heated at 55°C for 2 hours and at 95°C for 5 minutes for inactivation of protease K. All samples will be stored in a freezer at -80°C before polymerase chain reaction (PCR) amplification. The HOMIM methodology will be used here was described in detail in a previous study. Briefly, a total of 400 16S rRNA-based, reverse-capture oligonucleotide probes targeting >300 bacterial taxa. 16S rRNA genes are PCR amplified from DNA extracts using 16S rRNA universal forward and reverse primers and labeled via incorporation of cyanine 3-deoxycytidine triphosphate in a second nested PCR. The labeled 16S amplicons will be hybridized overnight to probes on the slides. After washing, the microarray slides will be scanned and crude data will be extracted using software for microarray image analysis. Data will be normalized by comparing individual signal intensities to the average of signals from universal probes (Ahn et al., 2011; Colombo et al., 2012; Lourenco et al., 2014)

Statistical Analysis:

[name], Assistant Professor, Loma Linda University School of Dentistry, Department of Dental Research, will perform statistical analysis.

Power Analysis:

To detect a difference of 2 mm in average pocket depth between the Non HBO+SRP and HBO+SRP treatment groups and assuming a standard deviation of 1mm, the study would need to have 12 subjects in each group to have an 80% chance of detecting the stated effect, at an alpha level of 0.05.

Hypothesis Testing:

We plan to test our central hypothesis and thereby accomplish the objective of this objective of this application by pursuing the following specific aims:

1) Evaluate the effect of HBO therapy on clinical outcomes of SRP.

Our working hypothesis, based on previous studies on SRP as a current standard of care in the non-surgical periodontal therapy, is that SRP alone is not fully successful in restoring tissue health and clinical outcomes such as GI, PPD, CAL, and BOP. The HBO therapy with SRP may have a synergic effect on enhancing blood supply, osteogenesis, and promoting growth factor production and can cause significant enhancement on tissue healing and clinical periodontal outcomes.

Statistical analysis:

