Differences in pocket depth from baseline to 12 weeks between the Conventional Wound Healing group and Hyperbaric Therapy group will be analyzed using the repeated measures ANCOVA (Analysis of Covariance) procedure for paired observations. Periodontal clinical measures at baseline and later time-points will comprise the dependent variables. The ANCOVA procedure will help to account for patient differences in demographics and other clinical factors at baseline while also adjusting for effects of confounding factors.

2) Examine the effect of the HBO therapy on subgingival microbial profile.

Our working hypothesis, based on initial effect stage of HBO therapy, is significant reduction and low levels of anaerobes bacteria persist after 3 months of combination therapy compare with only current standard periodontal treatment.

Statistical analysis:

Differences in bacterial counts from baseline to 12 weeks between the Conventional Wound Healing group and Hyperbaric Therapy group will be analyzed using the repeated measures ANCOVA (Analysis of Covariance) procedure for paired observations. Bacterial counts as measured at baseline and later time-points will comprise the dependent variables. The ANCOVA procedure will help to account patient differences in demographics and other clinical factors at baseline while also adjusting for effects of confounding factors.

Potential difficulties and limitations:

Antibiotic medications:

Antibiotic medications used in conventional wound care may influence the clinical and microbial factors we are measuring. To control for their potential influence, we will keep a log of all medications and doses. Subjects enrolled in the proposed study will not be asked to refrain from their antibiotics and other medications as part of their wound healing treatment prior to examination and sampling. We will collect our baseline data after the subjects start their medication regimen. Thus, the subgingival bacterial samples and clinical parameters recorded at baseline will account for antibiotic use prior to periodontal intervention. Furthermore, in our statistical analysis we will adjust for the number and class of medications.

Study Design: We elected to go for a longitudinal observational design because of budget limitation. Our objective is to collect pilot data to enable us to seek external funding for a fully powered “Randomized Clinical Trial”.

References:

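### The plan sets no limit on joint covariate adjustment, which includes number and class of medications, yet the sample size allows for no covariates; a full coding could take power below the stated 80%

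*Combined protocol and SAP*

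**What the plan says.** Under Hypothesis Testing, the statistical analysis paragraphs for both aims use a repeated measures ANCOVA from baseline to 12 weeks. Baseline and later values together form the dependent variables. The procedure "will help to account for patient differences in demographics and other clinical factors at baseline while also adjusting for effects of confounding factors". No variable is named there.

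Under Potential difficulties and limitations, the paragraph on antibiotics adds a firm commitment: "Furthermore, in our statistical analysis we will adjust for the number and class of medications". The classes and their coding are not given.

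The candidate variables can be read from Subject Characteristics, where "demographic data (age, gender, ethnicity, smoking history, alcohol use history, BMI, current medication list) and oral health habits will be obtained". HbA1c is measured as well.

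The Power Analysis is a plain two-group comparison. Its target is stated as "To detect a difference of 2 mm in average pocket depth between the Non HBO+SRP and HBO+SRP treatment groups". With the SD taken as 1 mm and alpha as 0.05, it concludes that "the study would need to have 12 subjects in each group to have an 80% chance of detecting the stated effect". It mentions no covariates. Six further subjects are recruited to cover attrition, so the Study Plan shows 15 per group. Groups are formed by medical need, and controls are recruited later to match the HBOT subjects.

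**The concern.** Joint adjustment in a small study has two costs. Each parameter removes a residual degree of freedom. Each also overlaps with the group indicator, if only by chance, and this inflates the variance of the HBOT effect. In 24 subjects the second cost is the larger one.

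A medication-class term needs several indicators, and these subjects have diabetes and chronic wounds, so several classes are likely. Some of those indicators will be sparse. The estimate could then depend on how a few subjects are coded.

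Because the plan fixes neither the list nor the coding, models of very different precision would all comply with it, and the choice could be made after the data are seen. That matters for a pilot whose purpose is to supply an effect estimate for a larger trial.

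**Working it through.** **Inputs.** From the Power Analysis: difference 2 mm, SD 1 mm, 12 per group, alpha 0.05, power 80%. Assumed: a two-sided test, an SD that applies to the analysed quantity (the plan does not say whether final value or change), complete data at N = 24, and covariates that act on the change. With two time points, the group-by-time test is then a regression of change on group plus k covariate parameters.

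**1. The plan's own figure.** Normal approximation: n per group = 2 × (1.960 + 0.842)² × 1² / 2² = 3.9, so 4. By t test, 5 per group gives 79% and 6 gives 87.6%. At 12 per group, power is 99.7%. The stated 12 for 80% is not reproduced. For 12 per group to give 80%, the difference would have to be about 1.20 mm at SD 1 mm, or the SD about 1.67 mm at 2 mm.

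**2. Parameter count (assumed).** Age, gender, smoking history (current smokers are excluded, so never/former), alcohol, BMI and HbA1c take 6. Ethnicity takes 1 to 4, number of medications 1, and medication classes 2 to 10. The low end is 6 + 1 + 1 + 2 = 10 and the high end is 6 + 4 + 1 + 10 = 21, so roughly 10 to 20 before any oral health habits.

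**3. Formulas.** Residual df = 24 − 2 − k = 22 − k. Noncentrality = (2/1) × √(24/4) × √(1 − R²), where R² is that of group on the covariates. For covariates unrelated to group, R² follows Beta(k/2, (23 − k)/2), with mean k/23, and power is averaged over it. CI half-width = t(0.975, 22 − k) × 1 mm × √(1/12 + 1/12) / √(1 − R²), taken at the median R².

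Example at k = 11: median R² is 0.477 and t is 2.201, so the half-width is 2.201 × 0.408 / √0.523 = 1.24 mm.

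| k | Residual df | Power, 2 mm | Median half-width (mm) | Power if 12 per group truly gave 80% (about 1.2 mm) | Power, 2 mm, all 30 complete |
|---|---|---|---|---|---|
| 0 | 22 | 99.7% | 0.85 | 80% | over 99.9% |
| 3 | 19 | 99% | 0.91 | 73% | 99.8% |
| 11 | 11 | 87% | 1.24 | 48% | 97% |
| 13 | 9 | 79% | 1.41 | 40% | 95% |
| 14 | 8 | 73% | 1.52 | 36% | 93% |
| 17 | 5 | 50% | 2.11 | 23% | 86% |

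On the 2 mm inputs, power first falls below 80% at 13 parameters with N = 24 (83% at 12), and at 19 with N = 30 (78%).

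**4. Sensitivity.**
- If the covariates cut residual variance by 30%, power at 2 mm is 95%, 85% and 62% at 11, 14 and 17 parameters.
- If they track HBOT status and explain 70% of group membership, power is 70% at 8 parameters and 69% at 11. With up to 12 parameters, power reaches 80% or less once they explain about 60 to 64%.
- If they were exactly balanced between groups (R² = 0), only the df cost would remain, and power would be 99.3%, 98.9% and 97.1% at 11, 14 and 17.

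**The case against.** The strongest reply is that the parameter count is assumed. The ANCOVA sentence is a general description, and listing what is recorded is not a promise to enter every item at once. A count plus a few antibiotic indicators would satisfy the medication sentence. That stands: the plan does not fix the loss, it only permits it.

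Three stronger readings are tempting, and the documents do not support them.
- A reader might infer a term for every medication. All medications are logged, but the adjustment is for number and class.
- A reader might infer that the stated power is necessarily lost. On the plan's inputs, 11 parameters still leave 87%. However, that reserve exists only because the stated inputs do not match the stated 80%; it is not a planned allowance for covariates.
- A reader might infer that the group effect cannot be estimated. No standard error is left only at 22 parameters, and the effect itself fails in general only from 23. Even the high end of the assumed count stays below that.

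Matching would help if it succeeded, as the exact-balance figures show. Close balance on this many items with 12 to 15 per group is hard to count on when need for HBOT defines the groups. The six extra subjects are meant for attrition, so 24 remains the planned analysis number. Pilot status lowers the weight of power, but the wider intervals still weaken the estimate that the pilot is meant to deliver.

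Finally, adjustment is the main analytic defence in a non-randomised comparison, so a short list has a real price.

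**Conclusion.** The point holds in a conditional form. The plan commits to open-ended joint adjustment, including a term with several levels for medication class, and its sample size ignores all of it. With about 11 parameters the interval is roughly half as wide again (1.24 against 0.85 mm). From 13 parameters, power on the stated inputs is below 80%. At 17 the half-width of 2.11 mm exceeds the 2 mm target.

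These figures rest on 24 completers, an assumed coding, and covariates unrelated to group and outcome. The loss is smaller if the covariates predict outcome, are well matched, or all 30 subjects complete. It is larger if they track HBOT status, or if the true margin is the 80% that the plan states. Confidence is moderate, because the plan gives no count.

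**What to change.** In the statistical analysis paragraphs for both aims, replace the open adjustment with a short prespecified set and its coding. One example is baseline value of the outcome, baseline HbA1c and systemic antibiotic use (yes/no). In the antibiotics paragraph, drop the joint adjustment for number and class of medications; the antibiotic indicator keeps the concern that the paragraph raises.

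Restate the model as the 12-week value (or change) on group plus these covariates, so that baseline is not also a dependent variable. Tabulate the other characteristics by group, and add each one singly as a sensitivity analysis.

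Redo the power statement for this model from a difference, SD and sample size that agree. Three covariates leave 99% on the stated inputs. If 12 per group truly gives 80%, three covariates unrelated to outcome would leave about 73%, so the restatement is needed.

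The change is to wording plus one calculation. Its downside is that, with groups formed by medical need, confounding by the remaining factors is explored one at a time and not adjusted jointly.
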